12.2. Statistical Analysis of Efficacy

Primary and secondary efficacy analyses will be performed on the Per-Protocol population, defined as all randomized subjects who missed no more than 3 treatment visits, completed Visit 10 (primary analysis) and Visit 13 (secondary analysis), and who have not had a major protocol violation over that time period, including the use of a clinically relevant quantity of a prohibited medication as determined by the study Medical Monitor. No missing data imputation will be used for these analyses.

Visit 10 is considered to be the primary efficacy endpoint. In addition, some analyses will also be conducted at earlier and subsequent visits, and treated as exploratory analyses. Some sensitivity efficacy analyses may also be re-performed on the Intent to Treat population, defined as those randomized subjects who have at least one post-baseline visit with required efficacy data collection and who completed Visit 10 with required collection of efficacy data. For those analyses, missing efficacy data for intermediate visits will be imputed using the last observation carried forward (LOCF) procedure. A determination as to the performance of analyses using the Intent to Treat population will be based on the number and pattern of visits missed by randomized subjects. Exploratory analyses using models specified below may also be performed for separate age groups, depending on enrollment outcomes.

For all analyses, two-tail alpha will be set to 0.05 with no adjustment for multiple comparisons. ANOVAs and ANCOVAs will include Site in the model only if doing so improves the sensitivity of the model for comparing treatment groups.

After the last randomized subject has completed Visit 10 the database will be validated, locked through Visit 10 and unblinded for the purpose of analyzing efficacy data through Visit 10. Those analyses are not considered to be interim analyses as the results will be final. Data will continue to be collected through Visit 13 for all subjects, and the full database will subsequently be locked for efficacy analysis (including durability of response) beyond Visit 10, and for the analysis of safety and all other clinical data.

The primary efficacy analysis will be a comparison between treatment groups based on the mean change in Target Wart PWA from Baseline (Visit 2) to Visit 10, using Analysis of Covariance with Baseline PWA as the covariate.

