Page 45 of 53 Amendment 2 Version 3 Date: 05 December 2017 Secondary efficacy analyses will include comparisons between treatment groups based on the following: the proportion of subjects with the Target Wart Clear (PWA = 0) at Visit 10 using Fisher's Exact Test; the proportion of subjects with all treated warts Clear at Visit 10 using a Cochran-Mantel-Haenszel test stratified by number of treated warts; and the mean of per-subject percentages of treated warts that are clear at Visit 10 using Analysis of Variance. The number of treated warts Clear at Visit 10 will also be analyzed using a Cochran-Mantel-Haenszel test stratified by number of treated warts Clear at Visit 10 will also be analyzed using a Cochran-Mantel-Haenszel test stratified by number of treated warts.

Durability of response in the Active treatment group will be evaluated by calculating the proportion of those treated warts achieving a PWA status of Clear at Visit 10 which continue to maintain a PWA status of Clear at Visit 13. This analysis will be performed separately for Target Warts, and for all treated warts. The 95% confidence limits around the calculated proportions will also be calculated in order to estimate the population lower limit value of the observed sample proportions.

Exploratory analyses will be conducted using a subset of the above analysis models, based on the following baseline wart classifications: warts that are determined to be treatment-naive vs. recalcitrant.

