7.3. Analysis Populations and Disposition of Subjects

7.3.1. Analysis Populations

The Safety Population is defined as all subjects who received at least one application of study medication.

The Intent-to-Treat (ITT) population is defined as all subjects who were randomized, received at least one application of study medication and had at least one post-baseline efficacy evaluation. No data imputation will be used for missing data.

The Per-Protocol (PP) population includes all ITT subjects who completed Visit 10 with no major protocol violation and who missed no more than 3 treatment visits. For the Visit 13 analysis, the PP population must also have had a Visit 13.

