9. STATISTICAL ANALYSIS METHODS

9.1. Statistical Analysis of Efficacy Data

Primary and secondary efficacy analyses will be performed on the Per-Protocol population, defined as all randomized subjects who missed no more than 3 treatment visits, completed Visit 10 (and Visit 13 for purposes of the Visit 13 analysis), and who have not had a major protocol violation over that time period including the use of a clinically relevant quantity of a prohibited medication as determined by the study Medical Monitor. No missing data imputation will be used for these analyses.

Visit 10 is considered to be the primary efficacy endpoint. In addition, some analyses will also be conducted at earlier and subsequent visits, and treated as exploratory analyses. Some sensitivity efficacy analyses may also be re-performed on the Intent to Treat population, defined as those randomized subjects who have at least one post-baseline visit with required efficacy data collection and who completed Visit 10 with required collection of efficacy data. For those analyses, missing efficacy data for intermediate visits may be imputed using the last observation carried forward (LOCF) procedure. A determination as to the performance of such analyses using the Intent to Treat population will be based on the number and pattern of visits missed by randomized subjects. Exploratory analyses using models specified below may also be performed for separate sub-groups, depending on enrollment outcomes.

For all analyses, two-tail alpha will be set to 0.05 unless otherwise specified, with no adjustment for multiple comparisons. ANOVAs and ANCOVAs will include Site in the model only if doing so improves the sensitivity of the model for comparing treatment groups.

After the last randomized subject has completed Visit 10 the efficacy data captured to date in the database will be validated, locked through Visit 10 and unblinded for the purpose of analyzing efficacy data through Visit 10. Those analyses are not considered to be interim analyses as the results will be final. Data will continue to be collected through Visit 13 for all subjects, and the full database will subsequently be locked for efficacy analysis (including durability of response) beyond Visit 10, and for the analysis of safety and all other clinical data.

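### Protocol 12.2 can be read as requiring Visit 13 completion for secondary comparisons that are all made at Visit 10, contrary to the SAP and to the protocol's own Visit 10 lock

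*Protocol*

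**What the plan says.** Protocol 12.2 states: "Primary and secondary efficacy analyses will be performed on the Per-Protocol population". Membership requires no more than 3 missed treatment visits, that the subject "completed Visit 10 (primary analysis) and Visit 13 (secondary analysis"), and that subjects be ones "who have not had a major protocol violation over that time period". On missing data: "No missing data imputation will be used for these analyses".

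The same section then lists four secondary between-arm comparisons:

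- Target Wart clearance: "the proportion of subjects with the Target Wart Clear (PWA = 0) at Visit 10 using Fisher's Exact Test"
- all treated warts Clear at Visit 10 (stratified Cochran-Mantel-Haenszel)
- the mean per-subject percentage of treated warts Clear at Visit 10 (analysis of variance)
- the number of treated warts Clear at Visit 10 (stratified Cochran-Mantel-Haenszel).

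Durability of response (Clear at Visit 10 and still Clear at Visit 13) is the only listed analysis that needs Visit 13. It is an estimate with confidence limits in the active arm, not a comparison between arms.

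The SAP words the Visit 13 condition differently. Section 9.1 asks that subjects "completed Visit 10 (and Visit 13 for purposes of the Visit 13 analysis"). Section 7.3.1 says: "For the Visit 13 analysis, the PP population must also have had a Visit 13".

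Protocol 12.2 also locks and unblinds the efficacy data through Visit 10 once the last subject reaches that visit, and says: "Those analyses are not considered to be interim analyses as the results will be final". The protocol (Amendment 2) is dated 05 December 2017 and the SAP 21 November 2017.

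**The concern.** If the Visit 13 condition covers everything called secondary, a subject with a valid Visit 10 grade drops out of the Visit 10 clearance comparisons for missing Visit 13, or for a major violation after Visit 10. Membership would then depend on events after the outcome was measured.

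Those events could be related to the outcome. No wart is retreated from Visit 10 on (Protocol 4). Liquid nitrogen, over-the-counter products and other wart therapies stay prohibited during the study (7.8.3). A subject whose wart has not cleared plausibly has more reason to leave or to seek other treatment. Selecting on Visit 13 status could then amount to selecting partly on Visit 10 clearance.

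Two further consequences follow. The primary result and the secondary clearance result, for the same wart at the same visit, could rest on different subjects. And because the Medical Monitor decides what quantity of prohibited medication is clinically relevant, some decisions on membership could fall after the Visit 10 unblinding; the documents do not say whether that role stays blinded. The Intent-to-Treat re-analysis in 12.2 would keep these subjects, but it is optional.

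**Working it through.** **The plan's own figure.** The only design figure is power above 90% for the primary analysis (Protocol 12.1, SAP 7.1). It cannot be reproduced, because no effect size, standard deviation, clearance rate or dropout rate is given. For orientation, 60 per arm at two-sided 0.05 gives 90% power at a standardized difference of (1.960 + 1.282) × √(2/60) = 0.59. The point here does not depend on this.

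**The texts side by side.**

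| Analysis | Visit needed | Protocol 12.2, read literally | SAP 7.3.1 and 9.1 |
|---|---|---|---|
| Primary: change in Target Wart PWA | 10 | Visit 10 | Visit 10 |
| Four secondary between-arm comparisons | 10 | Visit 13 | Visit 10 |
| Durability, active arm | 10 and 13 | Visit 13 | Visit 13 |

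The documents differ only in the middle row.

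**Time at issue.** Visit 10 is Day 57 (window +4) and Visit 13 is Day 134 (window +7). The gap is 134 − 57 = 77 days by schedule, from 134 − 61 = 73 to 141 − 57 = 84 days with the windows. At the Visit 10 lock, Visit 13 status is not yet known for every subject, so the literal secondary set cannot be formed for results described as final.

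**Illustration.** About 120 evaluable subjects at 1:1 gives 60 per arm. All rates below are assumptions. Let c be true Visit 10 clearance, and let lc and lu be the fractions of cleared and uncleared subjects lost or excluded between Visits 10 and 13. The observed clearance is

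c(1 − lc) / [c(1 − lc) + (1 − c)(1 − lu)].

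Take c = 30% active and 10% vehicle: 18 cleared and 42 uncleared v 6 cleared and 54 uncleared, a difference of 20.0 points.

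| Loss pattern | Active | Vehicle | Difference (points) |
|---|---|---|---|
| A: lc 5%, lu 20%, both arms | 17.1/(17.1 + 33.6) = 17.1/50.7 = 33.7% | 5.7/(5.7 + 43.2) = 5.7/48.9 = 11.7% | 22.1 |
| B: lc 0; lu 10% active, 30% vehicle | 18/(18 + 37.8) = 18/55.8 = 32.3% | 6/(6 + 37.8) = 6/43.8 = 13.7% | 18.6 |
| C: lc 5%; lu 10% active, 30% vehicle | 17.1/54.9 = 31.1% | 5.7/43.5 = 13.1% | 18.0 |
| D: lc 5%; lu 30% active, 10% vehicle | 17.1/46.5 = 36.8% | 5.7/54.3 = 10.5% | 26.3 |
| E: 10% loss of everyone | 16.2/54 = 30.0% | 5.4/54 = 10.0% | 20.0 |

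**Precision.** With all 60 per arm, the standard error of the difference is √(0.30 × 0.70/60 + 0.10 × 0.90/60) = 7.07 points. In A it is √(0.337 × 0.663/50.7 + 0.117 × 0.883/48.9) = 8.07 points, about 14% larger. In E there is no bias, but the standard error grows by √(60/54) = 1.054, about 5%.

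**No true effect.** With 20% clearance in both arms and the losses in C, active is 11.4/54.6 = 20.9% and vehicle 11.4/45.0 = 25.3%, a spurious difference of about 4.5 points. Pattern D gives the same size with the opposite sign.

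**The case against.** The best defence is that the phrase was never meant to reach the Visit 10 comparisons. It pairs Visit 13 with a secondary analysis in the singular. Duration of response is a stated secondary objective (Protocol 3.1.2), and durability is the listed analysis that uses Visit 13. The lock text in 12.2 fits this reading: results through Visit 10 are final at the first lock, and durability waits for the second. The SAP states the workable rule twice. Its violation period follows the same logic, so for a Visit 10 analysis it would naturally end at Visit 10.

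Much of this stands. A reader might infer that subjects will in fact be removed from the Visit 10 results; the documents do not show that, only that the protocol's wording permits it. A reader might also infer that the protocol governs because it is 14 days later. Neither document says which takes precedence on analysis sets, and nothing visible shows that Amendment 2 introduced or changed this phrase. Nor do the documents support a flat statement that clearance would be inflated: no loss rates are given, and cleared subjects could equally be the ones who skip follow-up, which would lower the rates.

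What does not fall away is the conflict. The sentence opens by covering primary and secondary efficacy analyses together, so the broad reading is the literal one. It yields a different analysis set from the SAP, and neither document says explicitly that the violation period for Visit 10 endpoints ends at Visit 10.

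**Conclusion.** Wrong as written, in a limited sense. Protocol 12.2 can be read as conditioning all secondary analyses on Visit 13, which contradicts SAP 7.3.1 and 9.1 and cannot be carried out at the protocol's own final Visit 10 lock. The likely intention is the SAP rule, so this is a definition to correct, not evidence that results will be biased. The primary analysis is unaffected.

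If the literal rule were applied, size and direction would depend on unknown loss patterns. Under the assumed 30% v 10% clearance with 60 per arm, the 20.0-point difference becomes 18.0 to 26.3 points across the patterns shown. The shifts in A and B (+2.1 and −1.4 points) are about 0.3 and 0.2 of the 7.07-point standard error. Loss unrelated to outcome and arm gives no bias, only less precision. The clearance rates, the loss rates and the link between clearance and loss are all assumptions.

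**What to change.** In Protocol 12.2, replace the Visit 10 and Visit 13 phrase with: *completed Visit 10; Visit 13 completion is required only for analyses of Visit 13 data*. This matches the SAP.

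In Protocol 12.2 and SAP 9.1, add that for any Visit 10 endpoint, major violations are judged only through Visit 10. Membership of the Visit 10 set can then be settled before the Visit 10 unblinding.

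The cost is one sentence in the protocol and one clause in the SAP. No new data, visits or analyses are needed.

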1. SYNOPSIS

	Protocol Number A-101-WART-202 Synopsis							
Protocol Number:								
	A Randomized, Double-Blind, Vehicle-Controlled, Parallel Group Study of A-101 Topical Solution Applied Once a Week in Subjects with Common Warts							
Sponsor:	Phase of Development:							
Aclaris	Phase 2							

Study Drug Description:

A-101 Solution (45%) is a hydrogen peroxide solution that will be supplied in a glass ampule with an applicator to be applied to common warts (verruca vulgaris) on the trunk or extremities.

The study drug, A-101 (hydrogen peroxide) 45% Topical Solution (hereafter referred to as A-101) is a colorless solution that must be stored at room temperature (15-25° C or 59 -77 ° F). The blinded vehicle solution is packaged to match the active study drug and will be stored under the same conditions. **Study Objectives:**

Primary:

The main objective of this study is to evaluate the clinical effect of A-101 45% vs Vehicle when applied to 1 common Target Wart (verruca vulgaris) on the trunk or extremities.

Secondary:

The secondary objectives of this study include:

- Evaluate the clinical effect of A-101 45% when applied to all treated Warts (Target plus Non-Target Warts)
- Duration of response in all treated Warts (Target Warts plus Non-Target Warts)
- Safety of A-101 45%

Study Design:

This is a phase 2, randomized, multicenter study to evaluate the safety and efficacy of A-101 45% vs Vehicle in subjects with common warts on the trunk or extremities. Subjects may have up to a total of 4 treated common warts located on their trunk or extremities. Investigators will be required to identify 1 Target Wart for treatment with A-101 study medication. An additional 3 Non-Target Warts may be treated and followed throughout the study protocol therapy. All identified Common Warts will be treated once a week for 8 weeks. Subjects will be followed for 3 months after the last weekly treatment.

Approximately 120 evaluable subjects will be randomized to one of 2 treatment arms in a 1:1 ratio. The duration of study participation is anticipated to be up to a maximum of 155 days per subject. All subjects will be followed for at least 12 weeks after the last study medication treatment.

Safety will be evaluated based on clinical laboratory studies (hematology and clinical chemistry), vital signs, assessment of local skin reactions (LSRs), assessment of adverse events (AEs), and concomitant medication review.

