The primary efficacy analysis will be a comparison between treatment groups based on the mean change in Target Wart PWA from Baseline (Visit 2) to Visit 10, using Analysis of Covariance with Baseline PWA as the covariate.

Secondary efficacy analyses will include comparisons between treatment groups based on the following: the proportion of subjects with the Target Wart Clear (PWA = 0) at Visit 10 using a one-tail Fisher's Exact Test; the proportion of subjects with the Target Wart Clear or Near-Clear (PWA = 0 or 1) at Visit 10 using a one-tail Fisher's Exact Test; the proportion of subjects with all treated warts Clear at Visit 10 using a Cochran-Mantel-Haenszel test stratified by number of treated warts; the proportion of subjects with all treated warts Clear or Near-Clear at Visit 10 using a Cochran-Mantel-Haenszel test stratified by number of treated warts; the proportion of subjects with all treated warts Clear or Near-Clear at Visit 10 using a Cochran-Mantel-Haenszel test stratified by number of treated warts; the mean of persubject percentages of treated warts that are Clear at Visit 10 using Analysis of Variance; the

mean of per-subject percentages of treated warts that are Clear or Near-Clear at Visit 10 using Analysis of Variance; and the mean of per-subject percent change from baseline PWA for treated warts using Analysis of Variance.

Durability of response in the Active treatment group will be evaluated by calculating the proportion of those treated warts achieving a PWA status of Clear at Visit 10 which continue to maintain a PWA status of Clear at Visit 13. This analysis will be performed separately for Target Warts, and for all treated warts. The 95% confidence limits around the calculated proportions will also be calculated in order to estimate the population lower limit value of the observed sample proportions.

Exploratory analyses may be conducted using a subset of the above analysis models, based on lesion sub-groups including body location, age, time to clearance, and also the following baseline wart classification: warts that are determined to be treatment-naive vs. recalcitrant.

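### Target Wart responder tests: Fisher's exact runs well below its nominal 5% and leaves out baseline grade; one two-sided stratified CMH test in both documents would recover some power

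*Protocol*

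**What the plan says.** Protocol 12.2 lists as a secondary comparison "the proportion of subjects with the Target Wart Clear (PWA = 0) at Visit 10 using Fisher's Exact Test". It names no tail there, but the same section states "For all analyses, two-tail alpha will be set to 0.05 with no adjustment for multiple comparisons".

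SAP 9.1 differs. It tests "the proportion of subjects with the Target Wart Clear (PWA = 0) at Visit 10 using a one-tail Fisher's Exact Test" and adds an endpoint absent from Protocol 12.2: "the proportion of subjects with the Target Wart Clear or Near-Clear (PWA = 0 or 1) at Visit 10 using a one-tail Fisher's Exact Test". Its general rule is "two-tail alpha will be set to 0.05 unless otherwise specified, with no adjustment for multiple comparisons", so it allows exceptions, but it never says whether the one-tail tests use 0.05 or 0.025. By their page footers, the SAP is dated 21 November 2017 and the Protocol amendment 05 December 2017, so the document without the exception is the later one.

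Neither document adjusts these tests for baseline PWA. Eligibility requires grade 2 or more on a 0 to 3 scale (Protocol 8.3), so baseline has exactly two levels. Baseline PWA is the covariate of the primary ANCOVA. CMH is already used for the all-warts endpoints, stratified by number of treated warts. On size: "Approximately 120 evaluable subjects will be randomized to one of 2 treatment arms in a 1:1 ratio".

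**The concern.** Fisher's test conditions on the total number of responders. With about 60 per arm and few responders, only a handful of tables are possible, and the rejection region falls well short of 5%. The unused error rate is lost power. The test also sets aside a two-level baseline value of the same wart that the primary model uses.

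At stake is the chance of showing a difference in Target Wart clearance. That outcome is easier to interpret than a mean change on a four-grade scale, and it defines the responders whose durability is followed to Visit 13. The loss cannot be pinned down while the two documents describe different tests.

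**Working it through.** **Figures the plan gives.** The only stated power is above 90% for the primary analysis (Protocol 12.1, SAP 7.1). No effect size or SD is given, so it cannot be reproduced. At 120/2 = 60 per arm, 90% power needs a standardized difference of (1.960 + 1.282) × √(2/60) ≈ 0.59. No power is stated for the Fisher tests.

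**Inputs.** From the documents: 60 per arm, two-sided 0.05, baseline grades 2 and 3. Assumed, because the documents give none: 55 per arm as a lower case, clearance rates, the grade mix, and the effect of grade on clearance.

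**One table by hand.** Take 60 per arm with 5 clear on active and 0 on vehicle.
- Fisher, one tail: (60·59·58·57·56)/(120·119·118·117·116) = 0.0287. Two-sided: 2 × 0.0287 = 0.057.
- Mantel-Haenszel, no continuity correction: z = (5 − 2.5)/√[60·60·5·115/(120²·119)] = 2.5/1.099 = 2.27, two-sided p = 0.023.

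The same data are non-significant by two-sided Fisher, significant by one-tail Fisher at 0.05, non-significant at one-tail 0.025, and significant by the two-sided Mantel-Haenszel test.

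**True size at 60 per arm.** Sum the two binomial probabilities over every table with p at or below the nominal level:

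| Common rate | Fisher two-sided 0.05 | Fisher one-tail 0.05 | Fisher one-tail 0.025 | Unstratified Mantel-Haenszel, two-sided 0.05 |
|---|---|---|---|---|
| 5% | 1.05% | 1.5% | 0.5% | 4.6% |
| 10% | 2.2% | 2.8% | 1.1% | 5.0% |
| 20% | 2.8% | 3.2% | 1.4% | 4.6% |
| 30% | 3.1% | 3.2% | 1.5% | 4.8% |
| 40% | 3.2% | 3.8% | 1.6% | 5.0% |

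At rates of 3% or less, two-sided Fisher is below 0.4%. In simulation, two-sided CMH stratified by baseline PWA ran at 4.5 to 5.3%.

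**Stratified statistic.** z = Σ(aₖ − n₁ₖtₖ/Nₖ) / √Σ[n₁ₖn₀ₖtₖ(Nₖ − tₖ)/(Nₖ²(Nₖ − 1))], with k = grade 2, 3.

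**Power by exact enumeration (60 per arm, two-sided 0.05).** The last column is simulated, with an assumed 60% at grade 2 and odds ratio 0.2 for clearing (grade 3 v grade 2):

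| Vehicle v active | Fisher | Unstratified Mantel-Haenszel | Stratified CMH |
|---|---|---|---|
| 5% v 20% | 63% | 73% | 75% |
| 5% v 25% | 84% | 90% | 91% |
| 10% v 25% | 49% | 58% | 61% |
| 10% v 30% | 73% | 79% | 83% |
| 15% v 35% | 65% | 72% | 76% |
| 20% v 40% | 60% | 67% | 72% |

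Fisher to Mantel-Haenszel is 5 to 10 points; stratifying adds 1 to 5 more at this strong grade effect. At odds ratios of 1 to 0.4, stratifying adds 0 to 2.

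**Power by simulation with rates set by grade (50% at grade 2).** Rates are for grade 2/grade 3:

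| Vehicle v active | Per arm | Fisher two-sided | Unstratified Mantel-Haenszel | Stratified CMH | Fisher one-tail 0.05 |
|---|---|---|---|---|---|
| 10%/2% v 32%/14% | 55 | 65% | 75% | 76% | 77% |
| 10%/2% v 32%/14% | 60 | 70% | 78% | 80% | 81% |
| 15%/5% v 45%/20% | 55 | 78% | 85% | 86% | 87% |
| 15%/5% v 45%/20% | 60 | 82% | 87% | 89% | 90% |

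Gains of stratified CMH over two-sided Fisher: 76 − 65 = 11, 80 − 70 = 10, 86 − 78 = 8 and 89 − 82 = 7 points. At higher response (30%/20% v 60%/50%) the gain is 3 to 4.

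**Extremes (60 per arm, unstratified Mantel-Haenszel minus Fisher).** 5% v 40%: 0.1 point. 5% v 30%: 2 points. 2% v 12%: 18 points.

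**One-tail readings.** At 0.025, Fisher's power equals the two-sided figures, so the whole gap remains. At 0.05, it matches two-sided stratified CMH to within about 2 points. Compared like for like with a one-sided stratified CMH at 0.05, Fisher still trails by roughly 1 to 10 points.

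**The case against.** Fisher's test is valid, and an exact test is a defensible choice for sparse counts. Conservatism cannot create false positives, which has some value in a plan with no multiplicity adjustment. These are secondary endpoints in a phase 2 trial with no power stated for them. All of this stands, and it makes the point one of efficiency. Exactness does not require the full loss, though: Boschloo's test, also exact, recovers 3 to 5 points over the 5 to 20% vehicle-rate scenarios.

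The SAP's one-tail wording is the strongest reply. At 0.05 it leaves no meaningful gap against the proposed test. But a two-sided 0.05 test allows 0.025 in the favourable direction, and one-tail 0.05 nominally doubles that; its true size is 2.8 to 3.8% at common rates of 10 to 40%. The Protocol's rule for all analyses makes no such exception.

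Three stronger readings are tempting and not supported:
- **A fixed loss of 7 to 12 points.** That range follows from particular assumed rates. The documents give no clearance rates, grade mix or grade effect.
- **Omitting baseline grade is the main cause.** It accounts for 0 to 2 points in most scenarios. Neither document says grade predicts clearance; its place in the ANCOVA does not show that, and the existing CMH tests stratify by number of warts, not grade.
- **Low response rates apply to both endpoints.** Clear or Near-Clear may be much more frequent. At 30 to 40% Fisher's size is about 3%, and the gain is likely to be at the lower end.

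**Conclusion.** The point holds as an inexpensive efficiency improvement. Two-sided Fisher at 55 to 60 per arm runs at about 1 to 3% for common rates of 5 to 40%; this follows from the sample size and the test. The power gain from a two-sided CMH test stratified by baseline PWA depends on assumed rates: roughly 3 to 12 points at moderate effects and about 0 to 18 over a wider range. Most of it comes from dropping Fisher's conservatism, and about 0 to 2 points (up to about 5 if grade is strongly prognostic) from stratifying.

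The conflict between the two documents over tails, and the missing one-tail level, must be settled first, because the gap is full at 0.025 and closes at 0.05. A reader might infer that the trial's stated power or the validity of its results is in doubt. Neither is: the figure above 90% concerns the primary ANCOVA, which is unaffected.

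**What to change.** Before the database is unblinded at Visit 10, put the same text in Protocol 12.2 and SAP 9.1:
- Compare Target Wart Clear, and Clear or Near-Clear, at Visit 10 with a two-sided CMH test at 0.05, stratified by baseline Target Wart PWA (2 v 3), without continuity correction.
- Report the common risk difference with its 95% CI. Neither document currently names an effect estimate for these comparisons.
- Keep two-sided Fisher as a sensitivity analysis and remove the one-tail wording.
- If an exact stratified test is wanted for very sparse tables, fix the expected-count threshold in advance; otherwise leave it out, so that the choice of test does not depend on the data.

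The cost is a wording change in both documents and a few lines of code, with no new data or visits. The downside is an asymptotic p-value in the main test. Its size was 4.5 to 5.3% in the stratified simulations; the unstratified version reached 5.5% at a common rate of 50% with 60 per arm.
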